3.3 Subject Data and Study Conduct

3.3.1 Subject Disposition

Counts and percentages of subjects who were screened (signed informed consent), discontinued early during screening (screen failures), and enrolled will be summarized in total based on all screened subjects.

Counts and percentages of subjects who were enrolled, started Remodulin, began transition to Orenitram, completed transition to Orenitram, had to return to Remodulin, discontinued study drug prior to Week 16 visit assessments, and completed the study will be summarized based on all enrolled subjects. Reasons for early discontinuation from the study will also be summarized.

3.3.2 Protocol Deviations

The following listings and summary table will be provided for Safety Population:

- Listing of Entry Criteria.
- Listing of Entry Criteria Violations. The status of the entry criteria will be listed for all subjects. The listing will include the date of the initial screening assessment and a list of any specific entry criteria that were not met.
- Summary of Entry Criteria Violations. If a sufficient number of violations occur, then the compliance to each criterion will be summarized.

Additional protocol deviations not captured in the CRF may be tabulated and listed based on criteria to be determined upon preparation of the final study report.

3.3.3 Analysis Populations

Counts and percentages of subjects in each of the 3 analysis populations (see section 3.2) will be summarized.

3.3.4 Demographic and Baseline Characteristics

The following demographic and Baseline characteristics will be summarized for each of the 3 analysis populations (see section 3.2):

- Sex
- Age
- Race
- Ethnicity
- Height (cm)
- Weight (kg)
- Body mass index (BMI) (kg/m²)
- Counts and percentages of subjects by PAH etiology will be provided. Days since initial PAH Diagnosis (as defined by RHC) will be summarized. Day of initial PAH Diagnosis will be imputed to the 15th if missing.

3.3.4.1 Hemodynamics

The following Right Heart Catheterization (RHC) parameters will be summarized for each of the 3 analysis populations:

Mean pulmonary arterial pressure (mPAP) (mmHg)

- Pulmonary artery wedge pressure (PAWP) (mmHg)
- Left ventricular end diastolic pressure (LVEDP) (mmHg) (if available)
- Cardiac Index (L/min/m²)
- Heart Rate (beats/min)
- SAPs (mmHg)
- SAPd (mmHg)
- SAPm (mmHg)
- PAPs (mmHg)
- PAPd (mmHg)
- RAPm (mmHg)
- PVR (Wood Units)
- PCWPm (mmHg)
- SaO2 (%)
- SvO2 (%)
- CO Thermodilution (L/min)
- CO Fick (L/min)
- BSA (m²)

3.3.4.2 REVEAL 2.0 Risk Score

The following parameters, which are the components of the REVEAL 2.0 risk score, will be summarized for each of the 3 analysis populations at Baseline:

- WHO Group [APAH-CTD (+1), APAH-PoPH (+3), FPAH (+2), Other (+0), Not Available (+0)]
- Sex and Age [Male Age > 60 yrs (+2), No (+0)]
- eGFR (<60 mL/min/1.73m² or (if eGFR unavailable) renal inefficiency (+1), No (+0), Not available (+0)]
- NYHA/WHO Functional Class [I (-1), II (+0), III (+1), IV (+2)]
- Systolic blood pressure (SBP) [SBP < 110 mmHg (+1), ≥ 110 mmHg (+0)]
- Heart Rate (HR) [HR > 96 BPM (+1), ≤ 96 BPM (+0)]
- All-cause Hospitalizations within 6 months [Yes (+1) | No (+0)]
- 6-Minute Walk Test [< 165 m (+1), 165 m to 319 m (+0), 320 m to 439 m (-1), ≥ 440 m (-2)]
- NT-proBNP [NT-proBNP < 300 pg/mL (-2), NT-proBNP 300 to 1099 pg/mL (+0), NT-proBNP ≥ 1100 pg/mL (+2)]
- Echocardiogram [Mild, Moderate, or Severe Pericardial Effusion (+1), Trace or No Pericardial Effusion (+0), Not Available (+0)]
- Pulmonary Function Test [% predicted DLCO < 40% (+1), ≥ 40% (+0), Not Available (+0)]
- Right Heart Catheterization mRAP [mRAP > 20 mmHg (+1) | ≤ 20 mmHg (+0) | Not Available (+0)]
- Right Heart Catheterization PVR [PVR < 5 Wood units (-1) | ≥ 5 Wood units (+0) | Not Available (+0)]

REVEAL 2.0 risk score is also an exploratory efficacy endpoint and will be summarized at the Transition Visit and Week 16. Change from Baseline to Transition Visit, Baseline to Week 16, and Transition Visit to Week 16 will also be summarized.

3.3.5 French Non-invasive Risk Score

The French non-invasive method is performed according to the 2015 ESC/ERS pulmonary hypertension guidelines (Boucly 2017). This method evaluates the number of low-risk criteria using 3 modifiable clinical parameters, which are defined as the following:

- 1) WHO functional class I or II
- 2) 6-minute walk distance >440 meters
- 3) NT-proBNP <300 ng/L

The number of low-risk criteria is counted and thus, a patient can possess 0 to 3 low-risk criteria. The French non-invasive risk score is an exploratory efficacy endpoint and will be summarized for each of the 3 analysis populations at Baseline, the Transition Visit, and Week 16. Change from Baseline to Transition, Baseline to Week 16, and Transition to Week 16 will also be summarized.

3.3.6 Concomitant Medications

Concomitant medications will be coded to anatomical therapeutic chemical (ATC) class and preferred term using the WHO Drug Dictionary version WHO-DDE B2, Mar 2017E. For summary purposes, medications will be considered as concomitant medications if they were taken at any time after the first dose of Remodulin (i.e. were ongoing or started after the first dose of Remodulin).

If a medication has incomplete start or stop dates, dates will be imputed to determine whether a medication should be considered prior or concomitant. If a medication start date is incomplete, the first day of the month will be imputed for missing day and January will be imputed for missing month. If a medication stop date is incomplete, the last day of the month will be imputed for missing day and December will be imputed for missing month. Incomplete start and stop dates will be listed as collected without imputation.

Counts and percentages of subjects taking concomitant medications by ATC class and preferred term will be summarized based on the Safety Population.

Counts and percentages of subjects' prior and current PAH background therapy (PDE5-I/sGC alone; ERA alone; PDE5-I/sGC+ERA; none) will be summarized by PAH medications separately based on the Safety Population.

3.3.7 Study Drug Exposure

A listing of Orenitram and Remodulin dose levels for each subject at each timepoint will be provided by visit.

A summary of Orenitram and Remodulin dose levels at each study visit will be provided for the Safety Population. Summary of dose levels at each study visit will also be provided for patients who transition at week 2, week 4, and week 8 separately. Change from baseline Remodulin dose levels will also be provided.

Days of exposure to study drug (Remodulin and Orenitram) will be calculated as date of last dose of study drug – date of first dose of study drug + 1. Note that the exposure calculation is intended to describe the length of time a subject was exposed to study drug and therefore does not take study drug interruptions into account. Days of exposure to study drug will be

summarized based on the Safety Population with descriptive statistics and with counts and percentages of subjects with exposure in the following categories:

- <4 weeks (<28 days)
- 4 -<8 weeks (28 55 days)
- 8 <12 weeks (56 83 days)
- 12 <16 weeks (84 111 days)
- ≥16 weeks (≥112 days).

Days of exposure to Remodulin and Days of exposure to Orenitram will also be summarized in the same way.

Number and percentage of subjects who initiated Remodulin in an inpatient vs. outpatient setting will be summarized.

Number and percentage of subjects who initiated Remodulin via IV or SC routes will be summarized

Number and percentage of subjects who switched between IV and SC routes for Remodulin will be summarized

For patients initiating Remodulin in the inpatient setting, the Remodulin dose at discharge will be summarized.

Number and percentage of subjects who initiated transition from Remodulin to Orenitram in an inpatient vs. outpatient setting will be summarized.

Summary statistics will be provided for:

- Time to Transition to Orenitram, calculated as date of first dose of Orenitram date of first dose of Remodulin + 1
- Duration of inpatient stay (for applicable subjects) for Remodulin initiation
- Duration of transition (days receiving both Remodulin and Orenitram)
- Duration of inpatient stay (for applicable subjects) for transition to Orenitram
- Dose of Remodulin (ng/kg/min) at Transition Visit
- Prescribed total daily dose of Orenitram (mg) at the Post-Transition visit

All the above summaries will be based on the Safety Population.

3.4 Efficacy Assessment

Efficacy data will be summarized as specified in 3.4.1 and 3.4.2. The Week 16 visit and early study withdrawal will be reported separately in the efficacy tables.

The prescribed total daily dose will be used for the primary and secondary efficacy endpoints when applicable, unless otherwise specified.

3.4.1 Primary Efficacy Endpoint

The number and percentage of subjects achieving an Orenitram dose of 4 mg 3 times daily (TID) (or a total daily dose of 12 mg) or higher (or a dose of 0.057 mg/kg TID [or a total daily dose of 0.171 mg/kg] or greater for subjects <70 kg) will be summarized for Week 16 for the Per-Protocol population. Subjects with missing data for prescribed total daily dose at Week 16 will be considered as not achieving the primary efficacy endpoint.

This will be repeated for the Completer Population.

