10.3 ANALYSIS PLAN

No formal hypothesis is being tested. The efficacy and safety data in the study will be presented in summary tables and listings in the final clinical study report. Listings will be sorted by subject, visit, and time point assessment (if applicable). For summary tables, the data will be summarized by visits and time point assessment, if appropriate. For continuous variables, descriptive statistics will include the number of observations, mean, SD, median, minimum, and maximum. For categorical variables, descriptive statistics will include the frequency and percentage in every category. Details of efficacy and safety analyses are provided below. Further details will be documented in a statistical analysis plan.

The Safety Population is defined as all subjects in the study who receive study drug (Remodulin or Orenitram). All safety and efficacy analyses will be performed on the Safety Population.

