3.2 Analysis Populations

3.2.1 Safety Population

The Safety Population is defined as all subjects in the study who received study drug (Remodulin or Orenitram). All safety analyses will be performed on the Safety Population.

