3.2.2 Per-protocol Population

The Per-protocol Population is defined as all subjects in the study who received study drug without any major deviations (which may interfere with efficacy evaluation).

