3.2.3 Completer Population

The Completer Population is defined as all subjects in the study who complete the study without any major deviations (which may interfere with efficacy evaluation) and are receiving Orenitram at Week 16.

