3.4.1.1 Sensitivity analysis

To support the robustness and assess the sensitivity of the primary efficacy endpoint, the primary efficacy endpoint in 3.4.1 will be calculated using the actual dose taken for Orenitram dose (the sum of the morning, afternoon, and evening dose, where a missed dose is considered 0 mg). This analysis will be performed on both the Per-Protocol Population and the Completer Population.

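### The SAP moves the primary endpoint from the protocol's all-treated set to Per-Protocol and Completer sets, plans no all-treated version, and does not declare the change

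*SAP*

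**What the plan says.** Protocol 10.3 defines the Safety Population as all subjects who receive Remodulin or Orenitram, and then states: "All safety and efficacy analyses will be performed on the Safety Population".

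SAP 3.2.1 keeps the definition but narrows the use: "All safety analyses will be performed on the Safety Population". Efficacy is no longer mentioned. The SAP adds two sets:

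- Per-Protocol (SAP 3.2.2): "all subjects in the study who received study drug without any major deviations (which may interfere with efficacy evaluation".
- Completer (SAP 3.2.3): subjects who "complete the study without any major deviations (which may interfere with efficacy evaluation) and are receiving Orenitram at Week 16".

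Under SAP 3.4.1 the primary endpoint "will be summarized for Week 16 for the Per-Protocol population" and is repeated for Completers, with this rule: "Subjects with missing data for prescribed total daily dose at Week 16 will be considered as not achieving the primary efficacy endpoint". The sensitivity analysis in SAP 3.4.1.1 replaces the prescribed dose with the dose actually taken and leaves the sets unchanged: "This analysis will be performed on both the Per-Protocol Population and the Completer Population". The secondary endpoints (3.4.2) and subgroups (3.4.4) use the same two sets or parts of them.

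SAP Section 5 lists two changes from the protocol: an informal interim analysis, and about 35 evaluable subjects. It does not list the change of efficacy population.

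**The concern.** The primary objective is the Orenitram dose reached at Week 16 after Remodulin induction. Under the protocol, the denominator is everyone who started treatment. That includes subjects who never transitioned, went back to Remodulin, or stopped drug, all of which the protocol allows (3.6 and 6.1). In those subjects the strategy did not deliver the target dose, so they belong in the denominator.

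The SAP's two sets lose part of that denominator in different ways. The Completer set makes being on Orenitram at Week 16 an entry condition, and that is close to the outcome being measured. The Per-Protocol set keeps such subjects but removes major deviators, and the SAP does not itemise what counts as major. SAP 3.3.2 leaves the tabulation of deviations not captured in the CRF to be done "based on criteria to be determined upon preparation of the final study report". SAP 4.2 requires exclusions to be final before the pre-final outputs, but not before database lock. Because the study is open-label, the list can be settled with each subject's dose known.

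The study has no control arm and no test, so this percentage is the primary result. As planned, the version the protocol calls for would not be produced, and a reader of Section 5 would not learn that it had been replaced.

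**Working it through.** The plan states no figure to reproduce: there is no target rate, alpha, power or sample size computation. The check is a comparison of the sets, followed by an illustration.

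**Step 1. How the sets nest.** Completers are a subset of Per-Protocol, and Per-Protocol is a subset of Safety.

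- Subjects in Per-Protocol but not Completer did not finish the study or were not on Orenitram at Week 16. SAP 3.4 reports early withdrawal separately from Week 16, so early withdrawers have no Week 16 dose and count as failures. Subjects on Remodulin only, or on nothing, are also failures. The number of achievers *x* is therefore the same in both sets while the denominator can only shrink, so *x*/Completer ≥ *x*/Per-Protocol (one rare exception is given under the objection).
- Subjects in Safety but not Per-Protocol are the major deviators. They may or may not have reached the dose, so the Per-Protocol figure can lie above, below or at the Safety figure. With no deviators the two are equal.

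**Step 2. Each set against Safety.** Assumptions, none of them given by the documents for this use:

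- 35 subjects in the analysed set. The number is borrowed from the SAP's evaluable target; neither set is defined by it.
- 28 achievers, so 28/35 = 80.0%.
- 5%, 10%, 15% or 20% of treated subjects left out. Treated N = 35/(1 − d) = 36.8, 38.9, 41.2, 43.8, rounded to 37, 39, 41, 44, so k = 2, 4, 6, 9 are excluded.

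The Safety percentage lies between 28/(35 + k), if none of the excluded reached the dose, and (28 + k)/(35 + k), if all did.

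| Excluded k | Treated N | Safety, none achieved | Safety, all achieved |
|---|---|---|---|
| 0 | 35 | 80.0% | 80.0% |
| 2 | 37 | 28/37 = 75.7% | 30/37 = 81.1% |
| 4 | 39 | 28/39 = 71.8% | 32/39 = 82.1% |
| 6 | 41 | 28/41 = 68.3% | 34/41 = 82.9% |
| 9 | 44 | 28/44 = 63.6% | 37/44 = 84.1% |

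For Completer exclusions due to not being on Orenitram at Week 16, the third column applies. For Per-Protocol exclusions, the whole range applies. At k = 9, Per-Protocol minus Safety runs from 80.0 − 63.6 = +16.4 points to 80.0 − 84.1 = −4.1 points. It is zero when 80% of the excluded reached the dose (7.2 of 9).

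**Step 3. All three sets on one dataset.** Assume 35 Completers with 28 achievers, 5 deviation-free subjects not on Orenitram at Week 16, and 5 major deviators.

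- Completer: 28/35 = 80.0%
- Per-Protocol: 28/40 = 70.0%
- Safety: 28/45 = 62.2% if no deviator reached the dose, 33/45 = 73.3% if all did

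**Step 4. Does another output supply the percentage?** SAP 3.3.7 summarises dose levels by visit for the Safety Population. The endpoint uses a weight-based threshold below 70 kg, so a dose summary does not give the percentage of achievers. The interim analysis (SAP 4.1) covers about 10 enrolled subjects with a Week 16 or early withdrawal visit, which is not the Safety Population either.

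**The case against.** The strongest reply is that little is at risk. The study is descriptive, with no test and no powered sample size, so neither error rates nor power change. Per-Protocol, the first-listed set, already keeps treated subjects who stop early and counts a missing Week 16 dose as failure. Its gap from Safety comes only from major deviators, whose number may be zero. Other outputs also help: counts in each population (3.3.3), disposition of all enrolled subjects (3.3.1) and individual doses by visit (3.3.7). A careful reader could bound the all-treated percentage from these. All of this is true and limits the size of the problem. But bounding or rebuilding a figure from listings is not the same as planning the protocol's primary analysis, and the change would still be undeclared.

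Four narrower points also have some force.

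- The endpoint uses the prescribed dose. A subject prescribed the target dose but in a short interruption at Week 16 could be a Per-Protocol achiever and not a Completer. This is possible but rare, and is the one exception to Step 1.
- The 16.4-point figure needs 9 of 44 treated subjects to be major deviators and none of them to reach the dose. It is an extreme of the illustration, not a forecast.
- SAP 3.3.2 concerns the tabulation of deviations and does not itself govern exclusions. SAP 3.2.2 and 3.2.3 do give a general criterion, interference with efficacy evaluation, but it is not itemised.
- Fixing exclusions before lock does not hide doses in an open-label study. The advance definition gives most of the protection, and the lock date gives an audit trail.

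**Conclusion.** The concern holds. The documents disagree on the analysis set for the primary endpoint, the all-treated percentage is not planned, and Section 5 does not disclose the change. These findings rest on the text alone and need no assumption.

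The size does rest on assumptions. With 80.0% in the analysed set and 2 to 9 treated subjects left out, a Completer figure overstates the all-treated percentage by 4.3 points (80.0 − 75.7) to 16.4 points when those left out are failures. The Per-Protocol figure could overstate by up to 16.4 points, understate by up to 4.1, or not differ. No one-way bias is claimed for Per-Protocol. This must be fixed because it concerns the study's main estimate and the protocol already states the set to use.

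**What to change.** - In SAP 3.4.1 and 3.4.1.1, make the Safety Population (all subjects who received Remodulin or Orenitram) the primary analysis set. Extend the existing missing-dose rule so that any subject without a Week 16 Orenitram dose, for whatever reason, counts as not achieving the endpoint.
- Keep Per-Protocol and Completer as supportive, and state that the Completer result is conditional on being on Orenitram at Week 16.
- Itemise the major deviations that lead to exclusion, and fix the exclusion list before database lock.
- Record in SAP Section 5 any efficacy analysis that still departs from Protocol 10.3, with the reason. As written, that includes the secondary endpoints and subgroups in 3.4.2 and 3.4.4.
- Optionally, give an exact 95% confidence interval beside the percentage.

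The cost is SAP wording and one extra table. No new data are needed. The headline percentage may be somewhat lower.

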3.4.1.1 Sensitivity analysis

To support the robustness and assess the sensitivity of the primary efficacy endpoint, the primary efficacy endpoint in 3.4.1 will be calculated using the actual dose taken for Orenitram dose (the sum of the morning, afternoon, and evening dose, where a missed dose is considered 0 mg). This analysis will be performed on both the Per-Protocol Population and the Completer Population.

3.4.2 Secondary Efficacy Endpoints

Secondary efficacy endpoints will be summarized by visit, as applicable. The change from Baseline at each visit will be summarized for each parameter. For study visits occurring after the Transition Visit, the change from Transition Visit will also be summarized for each parameter in addition to the change from Baseline. The continuous secondary endpoints will also be summarized on Transition Visit and X Weeks Post Transition Visit in addition to the nominal visits. The value of interest listed in section 2.3.2.2 will be provided.

- 6-Minute Walk Distance (6MWD)
 - The subjects receiving oxygen during the time of the test will be listed
 - The subjects having unusual circumstances that adversely affected the walk will be listed
- Heart rate recovery after 6MWD
- Borg dyspnea score
 - The Borg dyspnea scores and their respective shifts from baseline and Transition Visit will be summarized for each assessment (i.e. number and percent of subjects who improved, worsened, or had no change)
- World Health Organization (WHO) Functional Classification (FC)
 - The functional class values and their respective shifts from baseline and Transition Visit will be summarized for each assessment (i.e. number and percent of subjects who improved, worsened, or had no change)
- N-terminal pro-brain natriuretic peptide (NT-proBNP)
 - o The percent change from Baseline and Transition Visit will also be provided.
- · Echocardiographic parameters
- PAH symptom score
 - Severity grade values (i.e., 0, 1, 2, or 3) for each symptom of PAH (fatigue, dyspnea, edema, dizziness, syncope, chest pain, and orthopnea) will be listed for all subjects. The severity grades and their shifts from baseline and Transition Visit will be summarized for each assessment.
- Subjects' TSQM responses and Health-related quality of life (emPHasis-10) questionnaires

- The number and percentage of subjects that successfully transitioned to Orenitram at any dose and were successfully maintained on therapy at Week 16
- The number and percentage of subjects that improve in each of the following 4 individual clinical parameters (6MWD, NT-proBNP, WHO FC, right atrial area) to a lower risk stratum, as defined by the 2015 European Society of Cardiology guidelines, compared to Baseline will be provided for the Transition Visit and Week 16.
- The number and percentage of subjects that meet each of the following 4 individual clinical parameters in the low risk category, as defined by the 2015 European Society of Cardiology guidelines: 6MWD >440 meters, serum NT-proBNP <300 ng/L, WHO FC I or II, and right atrial area <18 cm². This will be provided for the Transition Visit and Week 16.
- The number and percentage of subjects that either achieve an Orenitram dose of 4 mg TID (or a total daily dose of 12 mg) or higher (or a dose of 0.057 mg/kg TID [or a total daily dose of 0.171 mg/kg] or greater for subjects <70 kg) or the percentage of subjects that achieve an Orenitram dose ≥2 mg TID and <4 mg TID (or a total daily dose ≥6 mg and <12 mg), with at least 2 of the following 3 clinical parameters: 6MWD increase by ≥10% or ≥30 meters from Baseline, serum NT-proBNP reduction >30% from Baseline, or WHO FC I or II. This will be provided for the Transition Visit and Week 16. This will be performed using both prescribed total daily dose as well as actual dose taken.

The continuous secondary endpoints may be analyzed using linear regression models with the endpoint [such as change in 6-Minute Walk Distance, change in log(NT-proBNP), and change in log(echocardiographic parameters) (performed by study sponsor at a later time) from Baseline to Transition Visit and Week 16] as the dependent variable and the baseline [or log(baseline)] value as a covariate. For endpoints modeled on the original scale, the predicted mean change from Baseline at the median baseline value will be provided, along with its associated standard error and 95% confidence interval. For endpoints modeled on the log scale, the predicted mean change from Baseline at the median log(baseline) value, with associated standard error and 95% confidence interval, will be back-transformed to the original scale and presented as the predicted geometric mean ratio to Baseline at the median baseline value. For each model fitted, the slope and its standard error and p-value will also be provided.

For patients in the Per-Protocol Population with a missing secondary efficacy endpoint at Week 16 for 6MWD, WHO FC, NT-proBNP or Echocardiographic parameters, the last observation carried forward (LOCF) method will be used, in addition to a separate complete case analysis. No imputation is needed for the Completer population.

The secondary efficacy endpoints will be summarized for the Per-Protocol Population, the Completer Population, and the subgroup of patients in the Completer Population who met the primary endpoint.

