10.2 SAMPLE SIZE

A sample size of approximately 30 evaluable subjects was set for feasibility and to ensure a reasonable dataset to evaluate the Orenitram dose achieved, the clinical response with an induction period with Remodulin, and to assess the safety and tolerability of Orenitram after induction therapy with Remodulin. No formal sample size computation was performed with respect to the primary endpoint.

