2.2.3 Sample Size Determination

A sample size of approximately 35 evaluable subjects (i.e. completing the week 16 study visit without any major deviations which may interfere with study endpoints) was set for feasibility and to ensure a reasonable dataset to evaluate the Orenitram dose achieved, the clinical response to Orenitram after an induction period with Remodulin, and to assess the safety and tolerability of Orenitram after induction therapy with Remodulin. No formal sample size computation was performed with respect to the primary endpoint.

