3.1.6 Hypothesis Testing

No formal statistical testing will be performed.

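### SAP 3.4.2 back-transforms the log-scale standard error along with the estimate and its limits; taken literally this gives a multiplicative factor, not a standard error of the geometric mean ratio

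*SAP*

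**What the plan says.** SAP 3.4.2 offers regression of the change on the baseline value as an option: "The continuous secondary endpoints may be analyzed using linear regression models". The examples on the log scale are "change in log(NT-proBNP), and change in log(echocardiographic parameters) (performed by study sponsor at a later time").

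Reporting then depends on the scale of the model:

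- **Original scale:** "For endpoints modeled on the original scale, the predicted mean change from Baseline at the median baseline value will be provided", together with its SE and 95% CI. Nothing is transformed, so the SE is an ordinary one.
- **Log scale:** the predicted mean change at the median log baseline, "with associated standard error and 95% confidence interval, will be back-transformed to the original scale and presented as the predicted geometric mean ratio" to Baseline.

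The slope, its SE and its p-value are also to be given for each model. Neither the SAP nor the protocol has a separate rule for the SE on the log scale, and neither mentions the delta method. SAP section 6 leaves programming detail to a separate document.

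**The concern.** In the log-scale sentence, one verb covers three quantities. The inverse of the log carries a point estimate and confidence limits to the ratio scale correctly, because it is monotone and these are positions on the scale. A standard error is a measure of spread, and its size on the new scale depends on where the estimate lies. Applying the same inverse to it gives exp(SE), which is not the SE of the ratio.

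What is at stake is the reading of a table. Under the original-scale rule the SE column holds an ordinary standard error, and a reader would expect the same in the log-scale output. Part of the log-scale work is left to the sponsor at a later time. Without a stated rule, two programmers could put different quantities under one column heading. The plan also states that "No formal statistical testing will be performed", so readers will rely on the estimates and their stated precision.

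**Working it through.** The plan states no SE, SD or geometric mean ratio for these endpoints, so there is no figure of its own to reproduce. The check is algebra followed by an illustration.

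**Inputs from the documents**
- Sample size: "A sample size of approximately 35 evaluable subjects" (SAP 2.2.3) and "A sample size of approximately 30 evaluable subjects was set for feasibility" (protocol 10.2). SAP section 5 records the change; both values are used as a range.
- Confidence level 95%, taken as two-sided.

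**Assumptions, not in the documents**
- SD of the log change: 0.4 to 1.0.
- True ratio to Baseline: 0.5 to 1.0.
- SE(log) = SD/√n. This approximates the planned prediction at the median log baseline, whose SE also depends on the residual SD and on how far the median lies from the mean.
- t on n − 2 degrees of freedom.

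**Formulas.** Let b be the log-scale estimate and s its SE.
- Ratio = exp(b).
- 95% CI = exp(b ± t·s), which is valid.
- SE of the ratio by the delta method ≈ exp(b)·s.
- Literal back-transform of the SE = exp(s).

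Since s > 0, exp(s) is always above 1. It does not involve b, so it is the same whatever the ratio. As n grows, s tends to 0 and exp(s) tends to 1, whereas a standard error must tend to 0. None of this needs an assumed figure.

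**One case in full** (n = 35, SD 0.7, ratio 0.70):
- s = 0.7/√35 = 0.118
- exp(s) = 1.126
- delta-method SE = 0.70 × 0.118 = 0.083
- 95% CI = 0.55 to 0.89

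**Range**

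| n | SD (log) | Ratio | SE(log) | exp(SE) | Delta-method SE | 95% CI |
|---|---|---|---|---|---|---|
| 35 | 0.4 | 0.5 | 0.068 | 1.070 | 0.034 | 0.436 to 0.574 |
| 35 | 0.7 | 0.7 | 0.118 | 1.126 | 0.083 | 0.550 to 0.891 |
| 35 | 0.7 | 1.0 | 0.118 | 1.126 | 0.118 | 0.786 to 1.272 |
| 30 | 0.7 | 0.7 | 0.128 | 1.136 | 0.089 | 0.539 to 0.909 |
| 30 | 1.0 | 1.0 | 0.183 | 1.200 | 0.183 | 0.688 to 1.454 |

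Over the whole grid exp(SE) runs from 1.07 to 1.20 and the delta-method SE from 0.034 to 0.183. Simulating the estimated ratio (400,000 draws per cell, normal log-scale error) gave SDs of 0.034 to 0.187, in agreement with the delta method.

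**With the covariate in the model.** One simulated regression on log baseline (n = 35, residual SD 0.7, prediction at the median) gave b = −0.520 and s = 0.110. The ratio is then 0.595, exp(s) = 1.116 and the delta-method SE = 0.595 × 0.110 = 0.065. The pattern is the same.

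**What exp(SE) does describe.** In the case worked in full, t = 2.03 and 1.126^2.03 ≈ 1.27. Then 0.70/1.27 = 0.55 and 0.70 × 1.27 = 0.89, which is the CI above. Used as a multiplicative factor it is coherent. Used as an additive SE it is not: 0.70 ± 2.03 × 1.126 gives about −1.59 to 2.99, and a ratio cannot be negative.

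**The case against.** The SAP does not say in so many words that the SE is exponentiated. The subject of the verb is the predicted mean change, and the SE and CI are attached to it by a comma. Back-transforming a standard error can also be understood as giving its delta-method value on the ratio scale, which would be legitimate. The separate programming document might say so. This stands in part: a delta-method reading is possible. But the sentence as written names one operation for all three quantities and gives no different rule for the SE, so a programmer who follows it would apply the inverse log throughout. The sentence needs correcting on either reading.

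A reader might infer two stronger things, and the documents support neither.

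- *That the printed SE would contradict the CI beside it.* It would not. The factor rebuilds that CI exactly when used multiplicatively. The fault lies in the label and in the additive reading that the label invites.
- *That precision would be misstated many times over.* Dividing 1.126 by 0.083 gives about 14, and over the assumed grid such quotients run from 6.6 to 32. But this divides a multiplicative factor, whose value for no uncertainty is 1, by an additive SE, whose value for no uncertainty is 0. It does not measure an error in any reported precision, and its size depends on the assumed SD and ratio.

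The remaining objection is about weight, and it stands. The models are optional, secondary and descriptive, and no test, endpoint or population depends on the back-transformed SE.

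**Conclusion.** The point holds as a faulty reporting rule of minor consequence. Applying the same back-transformation to the SE as to the estimate and the limits gives, if taken literally, a factor of about 1.07 to 1.20, where the SE of the ratio is about 0.03 to 0.18. These sizes rest on the assumed SDs, ratios and sample sizes listed above. That exp(SE) is not a standard error of the ratio rests on none of them.

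The geometric mean ratio, its 95% CI, and the slope with its SE and p-value are correct as planned. No conclusion about the primary endpoint is touched. The risk is confined to a misleading column in the NT-proBNP and echocardiographic outputs, if these models are run.

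**What to change.** Amend the log-scale sentence in SAP 3.4.2 so that only the predicted mean change and its two 95% confidence limits are exponentiated and presented as the geometric mean ratio with its CI. For the SE, choose one of the following and name it in the table heading:

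- leave it on the log scale, labelled as such; or
- report ratio × SE(log), labelled as a delta-method SE.

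Carry the same rule into the programming specifications, so that output produced later by the sponsor matches. The cost is one SAP sentence and a column label. No new data, analysis or design change is needed.
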